8. History of clinically significant cardiac arrhythmias or vasospastic disease (e.g., Prinzmetal's angina).
9. Abnormal EKG result that in the investigator's opinion is clinically significant.
10. Epilepsy or a history of seizures.
11. Enrolled in another clinical trial or have received any drug as part of a research study within 30 days prior to dosing.
12. Individuals who have a recent history of traumatic brain injury diagnosed by CT/MRI and have current sequela from prior brain injury, as determined by the study physician
13. Individuals with anemia

6. Drugs/ Substances/ Devices

- a. The rationale for choosing the drug and dose or for choosing the device to be used.

All cannabis will be obtained specifically for use in this study from the Federal Drug Supply System. For oral administration, brownies will be made by the BPRU pharmacy and will contain target THC doses of 0, 10mg, or 25mg, (e.g., 100 or 250mg of cannabis material that is approximately 10% THC by volume; or 250mg cannabis for which THC and other cannabinoids has been extracted). For vaporization, THC doses of 0, 5mg, and 20mg will be administered. Cannabis will be vaporized using a commercial vaporizer called The Volcano (Storz and Bickel, GmbH & Company (Oakland, CA). To preserve the blind, we will mix active and placebo cannabis so that the same amount of plant material is placed in the vaporizer at each session. For example, if we obtain cannabis with 10% THC, the placebo dose will contain 200mg cannabis for which THC and other cannabinoids has been extracted. The 5mg THC dose will contain 50 mg cannabis with 10% THC and 150mg cannabis for which THC and other cannabinoids has been extracted. The 20mg dose will contain 200mg cannabis with 10% THC. Selection of doses was conducted to balance participant safety and tolerability based on our previous experience, and to administer 2 active doses they are expected to produce subjective drug effects via each route of administration, but only one that produces significant impairment of performance ability. This will help test the sensitivity of the biological and behavioral assessments for detecting impairment versus discriminable drug effects. We have experience safely delivering acute cannabis doses within the range utilized in this study with healthy adult volunteers who are not frequent cannabis users.

Potential risks of consuming cannabis in the present study are stomach/gastrointestinal irritation and adverse effects associated with cannabis intoxication. We have considerable experience administering smoked, vaporized, and oral cannabis in our laboratory. Recently, using essentially the same protocol, we have administered up to 50mg THC via oral cannabis ingestion and up to 25mg THC via cannabis vaporization. Following 25mg oral THC administration to 23 healthy adults, one participant vomited and one participant experienced a brief period of anxiety. The participant who vomited experienced immediate relief of discomfort and the case of anxiety was resolved within about one hour of onset without the need for medical intervention. In both the oral cannabis study as well as a recently completed study of vaporized cannabis exposure, transient experiences of dizziness and nausea were reported by a minority of participants, the effects were dose-dependent, but did not result in the need for intervention and no participants withdrew participation as a result. In fact, half of the participants who completed the oral cannabis study volunteered for and completed the protocol extension involving smoked and vaporized cannabis administration one year later (those who elected not to return did so because of work conflicts or because they moved). By reducing the maximum doses administered in this study, we believe that we will still achieve our target behavioral outcomes, and maintain safety and tolerability of doses for study volunteers. That said, we still have adequate procedures in place to handle adverse events. The research space has multiple restrooms and bio-hazard waste containers for use in cases of vomiting. In cases

Date: May 18, 2018

Principal Investigator: [name]

Application Number: IRB00122849

where a participant experiences panic and or paranoid reactions, research staff will engage the person in relaxation exercises and will suspend research procedures until the volunteer has regained comfort. These types of effects are typically of short duration. Acute cannabis exposure is expected to result in a time-limited increase in heart rate and orthostatic hypotension. If heart rate increases above 120bpm, blood pressure increases above 160/90mmHg or drops below 90/50mmHg, a nurse practitioner or physician will be notified and will evaluate the study participant. The NP/MD will determine whether there is a need for urgent care versus continued observation and evaluation. In the case of an extreme adverse reaction, study staff will call 911 and EMTs will take participants across the street to the Johns Hopkins Bayview ER for treatment.

- b. Justification and safety information if FDA approved drugs will be administered for non-FDA approved indications or if doses or routes of administration or participant populations are changed.

Not applicable to this protocol.

- c. Justification and safety information if non-FDA approved drugs without an IND will be administered.

Not applicable to this protocol. An IND has been obtained for the administration of cannabis.

Study Statistics

- a. Primary outcome variable.

The primary outcome variables are the quantitative levels of THC and its metabolites in biological matrices (oral, urine, blood), subjective rating of "Drug Effect" on the DEQ, and performance on DRE and cognitive/psychomotor assessments.

- b. Secondary outcome variables.

Secondary outcome variables include subjective drug effect and mood ratings on additional items of the DEQ and vital signs.

- c. Statistical plan including sample size justification and interim data analysis.

The sample size estimate for this study was based on previous work in our laboratory evaluating dose effects of acute drug administration using a within-subjects design. A meta-analysis was previously conducted comparing the statistical power of 13 drug effect assessments from six dose-effect studies, with 14 participants each, evaluating a range of abused drugs in our laboratory (Felch, 1996). The analysis showed that average effect size for primary measures (i.e. subjective drug effect ratings, staff ratings and behavioral/cognitive performance measures) ranged from approximately 0.87 to 1.0. Based on this estimate of effect size, the proposed sample size of 20 should be adequate to assess the expected effects. This sample selection methodology has been consistent in our long history of studies investigating dose-effects comparisons of different drugs, which have demonstrated excellent external validity and have become the FDA recommended standard for human abuse liability assessment. Subjective drug effect and mood ratings, vital signs, DRE assessments and cognitive performance outcomes will be assessed using multiple regression analyses appropriate for repeated measures testing based on the final characteristics of the data set (e.g. normal distribution, skewness, kurtosis).

- d. Early stopping rules.

The study will be stopped if new information is learned that indicates a serious risk to study participants.

7. Risks

- a. Medical risks, listing all procedures, their major and minor risks and expected frequency.

Potential risks of cannabis exposure include dizziness, change in blood pressure, red or irritated eyes, drowsiness, easy laughing, euphoria, rapid heart rate, dry mouth, jitters, headache, nausea, vomiting, increased appetite, perceptual difficulties, memory lapse, hallucinations, confusion, depression, paranoid reaction, depersonalization, and rash. Additional potential risks of orally consuming cannabis are stomach/gastrointestinal irritation. We feel that the risk of serious adverse events related to cannabis exposure in this study is minimal, participants are experienced users and the doses we are administering are within the range by which most participants in our prior studies have had good tolerance to the drug.

Venous blood sampling may cause pain, tenderness, bruising, or bleeding at the needle puncture site. Some subjects may feel transient lightheadedness or dizziness, or lose consciousness (syncope), because of anxiety and vasovagal reaction. The only risk associated with oral fluid collection is dryness of the mouth.

A further risk is that participants may mistake the proposed studies as treatment or may delay treatment seeking in order to participate, although this is unlikely since we are targeting occasional users.

The cardiac sensor should not be worn by subjects with a pacemaker or defibrillators.

The eye-tracking camera will include exposure to flashing lights and light patterns. Some people with photosensitive epilepsy are susceptible to epileptic seizure or loss of consciousness when exposed to certain flashing lights or light patterns in everyday life. While the illumination of the eye tracking camera is continuous and invisible to the subjects, we will exclude from testing subjects with epilepsy or a history of seizure. The safety of the near-infrared lighting source was assessed using the guidelines set forth in the *IEC 62471/CIES009-2006, Photobiological Safety of Lamps and Lamp Systems Optical Standard*. The power output of the lighting source was measured with a commercial calibrated powermeter (Thorlabs PM100D) and used to determine irradiance and radiance. The standard specifies an irradiance safety limit of 100 W/m^2 , this is the maximum recommended irradiance for day-long continuous exposure by ACGIH, *American Conference of Governmental Industrial Hygienists*; the RTI custom system measured 44.1 W/m^2 . The standard also specifies a maximum radiance limit of $60 \text{ mW/mm}^2/\text{sr}$, and our system measured a radiance of $0.36 \text{ mW/mm}^2/\text{sr}$.

Breach of confidentiality about self-reported drug use, biological tests indicating recent drug use, and study participation is a risk.

- b. Steps taken to minimize the risks.

Participants are not a "vulnerable population" as defined by human subjects protection guidelines; that is, they are not minors, pregnant women, under legal coercion or restriction, or mentally impaired. They are competent adults who provide their voluntary informed consent. Participants will be recruited via media advertisements and posters that clearly state the nature and intent of the study. The consent process will inform the participant in detail of the procedures, time involvement, compensation, risk, and treatment options other than participation in our study. Particular emphasis will be given to providing information regarding the potential risks involved with taking the study drugs. Volunteers will also be instructed that they may withdraw from participation at any time without losing any of the compensation that they have earned to that point.

It is unlikely that any adverse event should arise that requires immediate medical or psychiatric treatment. However, in case of an adverse event, participants will be under the supervision of medical/nursing staff

Date: May 18, 2018

Principal Investigator: [name]

Application Number: IRB00122849

throughout the study. The medical and nursing staff at BPRU are trained in CPR and mobile emergency crash carts are available on the same corridor where all experimental procedures will be conducted. The research facility (BPRU) is located directly across the street from the Johns Hopkins Bayview Medical Center Emergency Department, and, in case of an adverse event, participants will be taken for immediate care. The Principal Investigator will be immediately notified of any serious adverse events that arise.

If participants develop nausea or vomiting after consuming cannabis, study staff will assist the affected participant(s) appropriately and contact a study physician located in the building should the PI and/or study staff decide the participant would benefit from medical attention.

Blood collection risk will be minimized by performing venipuncture while participants are sitting down, and by having them remain under staff observation until it is clear that no acute adverse effects occur as a result of the procedure. The risk of infection is negligible because standard sterile technique will be used. Placement of indwelling venous catheters poses a risk of infection or thrombophlebitis, which increases with duration of placement. This risk is minimized by use of careful sterile techniques and catheter placement by experienced nursing staff. The risk of anemia is negligible because the total amount of blood to be collected during the study (5 mL at screening and 288mL during sessions) is less than the amount (473 mL) collected within one hour during a single blood donation session. The amount of blood loss will be readily replaced without harm to study participants.

Individuals with a pace maker or defibrillator will not be given a heart rate monitor to wear during sessions. It is unlikely that any study volunteer with such devices would meet study eligibility requirements.

All advertisements and the informed consent process will clearly indicate that this research is designated only for those not seeking treatment, that participation is not a substitute for treatment, and that participation offers no clinical benefit. They will be clearly informed that they will be asked to ingest cannabis brownies and vaporized cannabis during their participation. Any participant who expresses an interest in receiving immediate treatment for cannabis or other substance use will be referred to a community treatment clinic. If this occurs during the study, their participation in the study will be terminated. As previously described, participants will be instructed that should they withdraw from the study at any point to pursue treatment they will still be compensated for their participation up until that point in the study.

Confidentiality will be maintained by using study specific identifiers, rather than participant names, on all study-related documents as possible, following standard human subjects practice for protecting PHI, and keeping all documents and video with PHI in secure physical and digital environments.

- c. Plan for reporting unanticipated problems or study deviations.

The PI will also follow ICH regulations (detailed in *Clinical Safety Data Management, Definitions, and Standards for Expedited Reporting*) regarding reporting of adverse events and all study deviations to the IRB and study sponsor.

- d. Legal risks such as the risks that would be associated with breach of confidentiality.

Participants' names will be recorded only on the screening, informed consent, and necessary medical and payment forms. Anonymous participant identification numbers will be used on all other forms and labeling of biological fluids and test results. Video footage of the field sobriety assessments will be stored internally on password protected computers and servers that conform to JHU IT standards and will not be shared outside the study team. All information gathered will be kept in locked research staff offices or file cabinets. All medical information obtained will be handled in accordance with HIPAA regulations. Only research staff will have access to participant records. The limits of confidentiality (e.g. suspected child abuse or neglect, or harm to self or others) will be discussed in detail with the participants during the

Date: May 18, 2018

Principal Investigator: [name]

Application Number: IRB00122849

informed consent process. To reduce the likelihood of patient records disclosure we have obtained a Certificate of Confidentiality.

- e. Financial risks to the participants.

This study does not involve patients receiving treatment; therefore, the financial risks are minimal. Participants will be fairly compensated for their time and effort in complying with the study protocol.

8. Benefits

- a. Description of the probable benefits for the participant and for society.

The primary benefit of the proposed research is in the knowledge gained regarding the relative biological, subjective and behavioral dose effects of exposure to cannabis administered orally, or via vaporization. The knowledge will be used to advise the establishment of new drug testing guidelines across different biological matrices, and will inform the relevance of oral administration vs. inhalation on interpretation of workplace or roadside drug testing. The study will also extend the extant literature investigating the acute dose effects of cannabis, including subjective effects, cognitive performance, and their correlation with biological cannabinoid levels. Because we anticipate relatively minor risks to these cannabis experienced study participants, we feel that the proposed research has a positive risk benefit ratio.

9. Payment and Remuneration

- a. Detail compensation for participants including possible total compensation, proposed bonus, and any proposed reductions or penalties for not completing the protocol.

All participants will be compensated \$30 for completing the screening assessment. Compensation for full participation is \$2030. Compensation of this magnitude is appropriate given the length and nature of this study.

Screening Visit:	\$30
Sessions:	\$300/session (\$1800 total)
Completion Bonus:	\$500
Total Compensation:	\$2330

10. Costs

- a. Detail costs of study procedure(s) or drug (s) or substance(s) to participants and identify who will pay for them.

The only direct costs to the participants will be their transportation to and from Bayview for each study visit. That cost has been factored into the compensation for participating.

Date: May 18, 2018
Principal Investigator: [name]
Application Number: IRB00122849

Reference List

- Ahmed, A.I.A., van den Elsen, G.A.H., Colbers, A., van der Marck, M.A., Burger, D.M., Feuth, T.B., Rikkert, & M., Kramers, C. (2014). Safety and pharmacokinetics of oral delta-9-tetrahydrocannabinol in healthy older subjects: A randomized controlled trial. *Eur. Neuropsychopharmacology.*, 24, (9), 1475-1482.

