Outpatient Discharge. Participants will be discharged after completing final assessments (approximately 8.5 hours post-exposure). In 3 prior studies conducted in our laboratory, this timeline has been adequate for healthy adults to resolve any effects from acute doses of cannabis that are equal to or greater than those used in the present protocol. If a study participant indicates the desire to be discharged from the study early, BPRU medical staff will review the self-reported rating of "drug effect" on the most recent subjective drug effect assessment and conduct a brief interview with the participant prior to discharge. At the end of each session, Study staff will compare vital signs and cognitive performance assessments with baseline data and engage in face-to-face conversation with the participant to ensure that they are fit to leave the unit. Cognitive performance tasks obtained include measures of psychomotor ability, working memory and divided attention. If the participant is able to cognitively engage with staff, vital signs are within normative range (HR < 100bpm, SYS BP < 160mmHg, DIA BP < 90mmHg), and performance is not below 10% of baseline, the participant will be cleared to leave without further evaluation. If any of these parameters are not met, medical staff will assess the participant and a formal field sobriety test will be conducted. If the participant reports a drug effect or exhibits behavior indicative of impairment/intoxication, the participant will be asked to remain at the BPRU until the drug effect subsides and they can pass a field sobriety test. If vital signs are out of range, then medical staff will evaluate and make a determination with regards to whether it is safe for participant to be discharged or remain under observation. Participants will not be allowed to drive home; instructions will be provided at the screening session regarding the need to make alternative transportation arrangements. If a participant fails to arrange a ride, taxi transportation home will be coordinated by study staff and provided free of charge.

Study Measures. A battery of measures will be used to assess participant characteristics and drug effects during the study.

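### The end-of-session discharge rule, read literally, passes a participant at one tenth of baseline performance; the evident intent is a loss of no more than 10%

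*Combined protocol and SAP*

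**What the plan says.** Section 4.a, Outpatient Discharge, sets the check made at the end of each session. It states that "Study staff will compare vital signs and cognitive performance assessments with baseline data" and talk with the participant face to face, "to ensure that they are fit to leave the unit". On what is compared, it says: "Cognitive performance tasks obtained include measures of psychomotor ability, working memory and divided attention".

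Clearance has three joint conditions: the participant can engage cognitively with staff, vital signs fall within stated limits, and the performance condition is met. The last of these, with its consequence, reads "performance is not below 10% of baseline, the participant will be cleared to leave without further evaluation".

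Failing any one has a defined consequence: "If any of these parameters are not met, medical staff will assess the participant and a formal field sobriety test will be conducted".

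**The concern.** A score that is not below 10% of baseline is, in plain arithmetic, a score of at least one tenth of baseline. Such a limit would send a participant for further evaluation only after performance had almost completely collapsed, which is at odds with a check on fitness to leave.

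This is the only numerical performance criterion for clearance. The ability to engage with staff is a judgement, and the hour-8 drug recognition (DRE) battery is not a stated discharge criterion. The line therefore decides whether a measured performance loss, on its own, leads to a medical assessment and a field sobriety test. Staff who applied the text exactly could clear someone the rule was meant to stop, and would not be deviating from the protocol.

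**Working it through.** **Inputs**

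- Pass mark and purpose: section 4.a, Outpatient Discharge, as quoted.
- Scores: section 4.a, Study Measures, performance assessments. The primary outcomes are accuracy for the DAT, accuracy and number of patterns completed for the DSST, and number of correct trials for the PASAT. Higher is better on all of them, so impairment shows as a fall below baseline.
- Timing: performance is measured before dosing at every session (Baseline Assessments) and again at hour 8 (performance assessments).

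**Step 1. The rule as written.** Let B be the baseline score, S the end-of-session score and L = 1 − S/B the proportional loss. The text passes S ≥ 0.10 × B, that is L ≤ 0.90.

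**Step 2. The rule as evidently intended.** A loss of no more than 10% means S ≥ 0.90 × B, that is L ≤ 0.10.

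**Step 3. Minimum passing scores.** The documents give no baseline scores, so these baselines are illustrative.

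| Baseline B | Minimum as written (0.10 × B) | Minimum as intended (0.90 × B) |
|---|---|---|
| 100 | 10 | 90 |
| 60 | 6 | 54 |
| 40 | 4 | 36 |

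**Step 4. Which losses the two readings treat differently.**

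| Loss | As written | As intended |
|---|---|---|
| 5%, 10% | pass | pass |
| 15%, 25%, 50%, 89% | pass | fail |
| 91% | fail | fail |

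The readings disagree whenever 0.10 × B ≤ S < 0.90 × B. The two pass marks differ by a factor of 0.90 / 0.10 = 9.

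**Step 5. Is it corrected elsewhere?** No other section restates or defines the performance limit. The rule also does not say whether it applies to each task or to a composite. Nor does it say which baseline is meant: the performance section also uses the word for the level reached in screening training, although the pre-dose session measurement is the natural reading.

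**The case against.** The strongest reply is that this is a slip of wording which staff would read sensibly. The stated purpose points to a 10% loss, and staff may already apply it that way. That is plausible, but the written text still says something else, and it is the text that governs a safety decision.

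The second reply is that other safeguards cover the gap. Much of this stands:

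- A separate provision says: "If the participant reports a drug effect or exhibits behavior indicative of impairment/intoxication, the participant will be asked to remain at the BPRU", and release then requires that the effect has subsided and a field sobriety test is passed.
- The Drug Effect Questionnaire is given at hour 8 and continues until no drug effect is reported.
- Discharge comes at about 8.5 hours, a period the protocol supports with three earlier studies in the same laboratory at doses at least as large as these.
- Participants may not drive home.

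So the wrong figure matters only for someone who has lost more than 10%, reports no effect, shows no impaired behavior, engages normally and has vital signs in range. The performance criterion is there for that person, so the safeguards reduce the risk without repairing the rule.

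Three stronger readings are tempting, and the documents do not support them.

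- A reader might infer that impaired participants would be released after the high-dose sessions, of which completers have 20 × 2 = 40. The Protocol Overview expects impairment from the high doses but does not place it at hour 8, and the discharge section expects effects to have resolved by then.
- A reader might infer that one tenth was a deliberate choice. Nothing in the plan argues for it.
- A reader might infer that low blood pressure goes unchecked, because the discharge limits are upper limits only: "vital signs are within normative range (HR < 100bpm, SYS BP < 160mmHg, DIA BP < 90mmHg". Section 6.a carries a separate trigger with no time limit: "If heart rate increases above 120bpm, blood pressure increases above 160/90mmHg or drops below 90/50mmHg, a nurse practitioner or physician will be notified". It still applies at hour 8, so that is not a defect.

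**Conclusion.** The concern holds as a wrong threshold in a safety rule. As written the pass mark is 0.10 × baseline, and the evident intent is 0.90 × baseline. The literal meaning is certain. The 10% margin is an inference from the section's purpose, because the plan never states it, and the investigators must confirm it.

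The size in practice is unknown. The documents contain no hour-8 scores, so the number of clearances that would change cannot be estimated, and the safeguards suggest that it is small. No effect on the trial's outcomes, sample size or analysis is claimed. The correction is recommended because the text defeats its own aim and is easily put right.

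**What to change.** Replace the performance condition with: *performance is no more than 10% below that session's pre-dose baseline on each of the DAT, DSST and PASAT primary scores*.

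The investigators should confirm three things:

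- the 10% margin;
- that the rule applies per task and not to a composite;
- which DSST outcome counts, accuracy or number of patterns completed, since the protocol names both as primary.

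The DRUID app is left out of this wording because the protocol states no outcome score for it.

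The cost is a short wording amendment. The session baseline and hour-8 scores are already collected. The downside is that ordinary variation will take some unimpaired participants past the 10% margin and send them to a medical staff assessment and a formal field sobriety test. The documents give no within-person variability for these tasks, so that rate cannot be estimated. A per-task rule will refer at least as many people as a rule requiring failure on all tasks, which is one reason the investigators should make that choice explicitly.
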